8.1 Summary of Participant Disposition

Participant disposition will be summarized overall, and by country, and will include the number of participants in each analysis set defined in chapter 6, and the number of participants in the APTS who

- completed the study
- withdrew from study

To assess the potential impact of COVID-19 on the visit structure, a table will be provided by visit for the visits that are changed from on-site to remote if applicable. The summary will be based on APTS.

8.2 Withdrawals

The number of participants who withdrew from study will be summarized by primary reason for withdrawal and all reasons for withdrawal.

Participants who withdrew from study will be listed and the listing will include the number of days since the first IMP until withdrawal from study, the number of days since the last IMP, and the primary reason for withdrawal, and all reasons for withdrawal.

Kaplan-Meier failure plots of time to withdrawal from study will be presented. The time will be calculated from the date of first dose of IMP to the date of the withdrawal from study or the date of the Completion Visit, whichever comes first. Participants who were in the trial until the Completion Visit or Week 48, whichever comes first, will be regarded as censored from that timepoint.

All tables, graphs, and listings will be based on the APTS.

9 Demographics and Baseline Characteristics

Demographics (sex, age, race, region, country); baseline characteristics (height, weight, and BMI); baseline disease characteristics; and baseline efficacy variables will be summarized.

Baseline disease characteristics comprise of prior preventive medications used, number of treatment failures and reasons for treatment failures for all and by prior preventive medications. Furthermore, family history of CH (yes/no), relatives with a CH diagnosis, time since first symptoms of CH, time since cCH diagnosis, any previous change over time for the CH phenotype, time since the beginning of the current period of attacks, duration of the last remission period (in weeks), usually have a remission period (yes/ no), length of remission period if applicable, ability to predict the start of attacks after a remission period (yes/no), seasonal beginning of cCH attack periods (yes/no), season where the cCH attack periods begin if applicable, usual duration of CH attack period (in weeks), usual start time of CH attacks (hourly intervals/unknown), usual number of CH attacks per day, usual duration of the attacks (in minutes), trigger factors (yes/no), which trigger factors if applicable, usual pain intensity, and the accompanying symptoms are also considered baseline disease characteristics. See [Panel 3](#) for more details regarding the categories.

Panel 3 Categories for baseline disease characteristics

Variable	Categories
Treatment failures	Lack of efficacy, safety/tolerability, contraindication, participant in remission period, other
Relatives with a CH diagnosis	Mother, father, sister, brother, mother's mother, mother's father, father's mother, father's father, daughter, son
Change over time for CH phenotype	No, from episodic to chronic, from chronic to episodic back to chronic
Length of remission period	<1 month, 1 month <= and < 2 months, 2 months <= and <= 3 months
Season where cCH attack periods begin	Spring, summer, autumn, winter, other
Trigger factors	Alcohol, sleep, stress, other
Usual pain intensity	No pain or barely any pain, mild pain, moderate pain, severe pain, excruciating pain

The eDiary reported baseline efficacy variables that will be summarized are the number of weekly attacks, number of times abortive medication (triptans and/or oxygen, oxygen, triptans) was used weekly, weekly integrated measure of frequency and intensity of attack related pain, average attack related daily pain score, and average pain per attack, which are all collected during the 28-day Screening Period.

The other baseline efficacy variables that will be summarized are: SIS domain scores, EQ-5D-5L descriptive items as well as the visual analogue scale (VAS) scores of the overall health state, and WPAI:GH2.0 sub-scores.

Concurrent as well as relevant past medical, neurological, and psychiatric disorders will be coded using the *Medical Dictionary for Regulatory Activities* (MedDRA) and summarized by SOC and preferred term.

A concurrent medical, neurological, or psychiatric disorder is a disorder that is ongoing at the Screening Visit. A past medical, neurological, or psychiatric disorder is a disorder that ended prior to the Screening Visit.

Social history will be summarized.

Demographics and baseline characteristics will be summarized based on the APTS, and baseline efficacy variables will be summarized based on the FAS.

10 Recent and Concomitant Medication

Recent and concomitant medication will be coded using the *WHO Drug Dictionary* (WHO-DD).

Medications will be classified according to the start and stop dates and summarized by anatomical therapeutic chemical (ATC) code level 4, and generic drug name. Handling of missing or incomplete dates is specified in section [23.4.3](#).

The following categories will be used:

- Prior: Medications with a start or stop date before first IMP infusion,
- Concomitant: Medications with a start date at or after the date of first IMP infusion, medications with a stop date at or after the date of first IMP infusion, medications with a start date before first IMP infusion and with no stop date (being ongoing at the end of the trial), and medications where both start and stop date are completely missing

The summaries will be repeated for CH medication (only prior), preventive medication, and transitional medication.

Transitional medications will be listed based on the APTS. The listing will include the generic drug name, indication, time since the first IMP, the duration, the start and end dates, and dosing information.

All disallowed medications will be listed based on the APTS. The listing will include the generic drug name, indication, time since the first IMP, the duration, the start and end dates, and dosing information.

The eDiary reported medications will be handled separately. For further details see section [13.5.8](#).

11 Exposure

The total number of infusions received, and total number of infusions completed as planned will be summarized.

Furthermore, for each infusion visit, the number of infusions received, completed as planned, temporarily interrupted, and lasted longer than 45(+15) minutes, as well as descriptive statistics for the duration of infusions and for the duration of the infusions that were temporarily or fully interrupted will be summarized.

Participants, who at any point during the trial received a different dose than what was planned, will be listed. The listing will include all infusion visits, dates of infusion visits, planned dose for the participant and actual dose received for the participant.

In addition, all infusion data will be listed, i.e. the start and stop time of the infusion and the duration of the infusion.

The number of participants with a 1-year exposure (for details see section [23.2.2](#)) will be summarized.

The summaries will be based on the APTS.

12 eDiary Compliance

The number and proportion of participants with eDiary data will be summarized and presented by 1-week intervals. The summary will for each week include the number of participants in the trial for that week, the number and percentages of participants with data for that week, and for weeks with daily registrations the percentages of participants with 4, 5, 6 and 7 days of data.

A participant will count as being in the trial for a week if (s)he has at least 1 day with eDiary data in that week.

The summary will be based on the APES.

13 Efficacy

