23.2.1.3 Imputation of Missing Post-baseline eDiary Assessments

The strategy of imputation of missing values is given by:

1. For each weekly score in the periods with daily entries in the eDiary, prorating is used to impute any missing data when data have been observed for at least 4 days in a week, to have full weekly scores
2. For each monthly score, prorating is used to impute any missing data when data have been observed for at least 2 weeks in a month (after prorating weekly scores), to have full monthly scores

For a 7-day weekly period where the eDiary is completed in at least 4 out of 7 days, the number of attacks will be calculated using prorating:

$7 * (\text{Reported number of daily attacks/Reported eDiary Days})$

For participants where the eDiary is completed in 3 days or less, the 7-day weekly observation will be set to missing.

For a 4-week monthly period where the eDiary is completed in at least 2 out of 4 weeks, the number of attacks will be calculated using prorating:

$4 * (\text{Number of weekly attacks/Reported eDiary Weeks})$

For participants where the eDiary is completed in 1 week or less the 4-week monthly observation will be set to missing.

Use of abortive medication is prorated using the same criteria and formulas as above where *Reported number of daily attacks* is replaced by *Reported number of daily times an abortive medication was taken* and *Number of weekly attacks* is replaced by *Number of weekly times an abortive medication was taken*.

The severity of attacks is prorated using the same criteria as above using the same formulas as in section [23.2.1.2](#).

The derivation of the three pain scores can be seen in [Panel 5](#). When calculating the average attack related daily pain and the weekly integrated measure of frequency and intensity of attack related pain, a value of 0 will be added to the nominator and count as a day in the denominator for days/weeks with 0 attacks. Furthermore, the weekly pain per attack is not defined for days/weeks with 0 attacks.

Panel 5 Definitions of Post-Baseline Pain Scores

	Daily eDiary	Weekly eDiary
Average attack related daily pain	Sum of the average daily pain across days with data/number of days with data	NA
Weekly pain per attack	Sum of pain across attacks/number of attacks	Pain
Monthly pain per attack	Sum of the weekly pain per attack scores/ number of the weekly pain per attack scores	

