23.4 Handling Missing or Incomplete Dates/Times

23.4.1 Withdrawal Date

Missing withdrawal dates will not be imputed and time to withdrawal from study or treatment will not be calculated for missing withdrawal dates.

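### The weekly eDiary compliance table takes its denominator from the diary itself, so the percentage with data is 100% by construction

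*SAP*

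**What the plan says.** SAP Section 12 (eDiary Compliance) sets out a table by one-week intervals. It says "The summary will for each week include the number of participants in the trial for that week", followed by "the number and percentages of participants with data for that week". For weeks with daily registration it adds the percentages with 4, 5, 6 and 7 days of data. Membership of the weekly count is then defined: "A participant will count as being in the trial for a week if (s)he has at least 1 day with eDiary data in that week". Section 12 closes by naming the analysis set: "The summary will be based on the APES". It names no other denominator and does not refer to withdrawal dates.

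Elsewhere the SAP tracks study status without using the diary. Section 3.3 defines withdrawal from study from eCRF data. For the Kaplan-Meier plot in Section 8.2, "The time will be calculated from the date of first dose of IMP to the date of the withdrawal from study" or to the Completion Visit, whichever comes first.

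**The concern.** A compliance percentage should compare those who supplied data with those who were due to supply it. Here the second group is defined by membership of the first. A participant who is still on study but skips the diary for a whole week leaves numerator and denominator together, just as a participant who has withdrawn does. The table cannot tell the two apart.

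On-study missingness is what a reader needs in order to judge the SAP's missing-data rules. Under Section 23.2.1.3, "For participants where the eDiary is completed in 3 days or less, the 7-day weekly observation will be set to missing". Monthly scores need at least 2 of 4 weeks. The response and conversion rules (23.2.1.7 and 23.2.1.8) need at least half the weeks observed, and the MMRM takes whatever remains. Months 2, 3, 5, 6, 8, 9, 11 and 12, which are 8 of the 12 months in the long-term estimand, consist entirely of weekly-entry weeks. Those are the weeks for which the table gives no other compliance percentage.

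**Working it through.** The plan states no compliance figure to reproduce. The main result is a set identity; the rest is illustration.

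**Inputs from the documents**
- Weekly-entry weeks 5–12, 17–24, 29–36 and 41–48 (SAP Section 2): 4 × 8 = 32.
- Daily-entry weeks 1–4, 13–16, 25–28 and 37–40: 4 × 4 = 16.
- Planned enrolment 125, with 100 expected to complete (SAP Section 20). These serve only to scale the examples.

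**Identity.** Let D be the number of participants with at least 1 day of diary data in a week. Section 12 sets the number in the trial equal to D. The number with data, in its ordinary sense, is also D. The percentage is D/D = 100% in any week where D > 0.

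**Weekly-entry week (assumed counts).** Suppose 70 entries arrive.

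| Still on study | True completion | In-the-trial denominator | APES denominator (125) |
|---|---|---|---|
| 70 | 70/70 = 100% | 70/70 = 100% | 70/125 = 56.0% |
| 85 | 70/85 = 82.4% | 100% | 56.0% |
| 100 | 70/100 = 70.0% | 100% | 56.0% |

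Neither denominator separates the three cases.

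**Daily-entry week (assumed rates).** Suppose 100 participants are on study, E of them have a wholly empty week, and each of the others completes each day independently with probability p. For X ~ Bin(7, p), the Section 12 percentage with at least 4 days is P(X ≥ 4)/P(X ≥ 1), whatever the value of E. The on-study percentage is (100 − E)% × P(X ≥ 4). With p = 0.9, P(X ≥ 4) = 0.997:

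| E | True, on-study | In-the-trial denominator | APES denominator (125) |
|---|---|---|---|
| 0 | 99.7% | 99.7% | 79.8% |
| 10 | 89.8% | 99.7% | 71.8% |
| 20 | 79.8% | 99.7% | 63.8% |
| 30 | 69.8% | 99.7% | 55.8% |

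With p = 0.7 and E = 20, the true figure is 69.9% and the in-the-trial figure is 87.4%.

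**Partly missed weeks.** For p = 0.9, 0.7 and 0.5, P(X ≥ 4)/P(X ≥ 1) is 99.7%, 87.4% and 50.4%. The day-count percentages therefore do respond to partial non-completion. What they cannot show is the wholly empty week.

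**The case against.** The strongest reply is that Section 12 bases the summary on the APES, a fixed set that does not depend on the diary. Where the SAP wants a denominator other than the analysis set it usually says so (Sections 14.2, 15 and 23.2.1.7). On that reading the percentage is not 100%, and the daily-entry figures do move with empty weeks, as the last column of the second table shows. But Section 12 does not name the APES count as the weekly denominator. If it were, the separate in-the-trial count would merely repeat the number with data, and every withdrawn participant would count as non-compliant. So the alternative reading shows the wording is open to dispute without making the table informative. Reading 'with data' as at least 4 of 7 days does not help either: Section 12 does not cite that rule, and it cannot apply to a single weekly entry.

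The second reply is that little depends on the table. This largely stands. The prorating rules and the MMRM use participant-level data. Weekly counts are printed, Section 8.2 gives a withdrawal listing and a Kaplan-Meier plot, and sites check compliance at every visit and phone contact. A reader could approximate on-study completion by hand. The reconstruction is imperfect, because Section 8.2 uses the APTS while Section 12 uses the APES, and Section 23.4.1 says "Missing withdrawal dates will not be imputed".

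**Conclusion.** The concern holds. Followed as written, Section 12 gives a percentage with data of 100% in every week, and for the 32 weekly-entry weeks that is the only compliance percentage in the table. In the 16 daily-entry weeks the 4-to-7-day percentages are informative about partial weeks but too high whenever on-study participants miss a whole week: 99.7% against a true 79.8% in the example with 20 of 100 empty.

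The 100% result rests on taking the in-the-trial count as the denominator, which is the only reading that gives that count a purpose. The sizes rest on assumed completion rates, since the documents give none. The effect is confined to a descriptive table. It should be corrected, but no efficacy or safety estimate depends on it.

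**What to change.** Define being in the trial for a week independently of the diary, and name that number as the denominator for all weekly percentages. For post-baseline weeks: first infusion received, and neither withdrawn from study nor past the Completion Visit by the start of the week. Participants withdrawn from treatment who remain in the study stay in the count. That definition is the essential change.

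Four additions would complete it:
- A rule for weeks cut short by withdrawal, such as leaving them out of the denominator and showing their number separately.
- A fallback for missing withdrawal dates, such as the last visit or phone contact in the eCRF.
- If screening weeks are tabulated, counting from the Screening Visit to first infusion or exit, including untreated APES participants. This matters less, because enrolment already requires diary entries on 24 of 28 days.
- In daily-entry weeks, reporting 0 days and 1–3 days alongside 4, 5, 6 and 7.

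The cost is a short paragraph in Section 12 and a little programming. For treated participants the dates are those Section 8.2 already uses; untreated APES participants and the last-contact fallback need additional dates. Reported compliance will fall wherever on-study participants miss whole weeks.

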13.1 General Efficacy Analysis Methodology

All confidence intervals (CIs) will be two-sided 95% CIs.

13.2 Testing Strategy

No formal testing will be done.

13.3 Analysis Methodology for the Primary Endpoints

There are no primary efficacy endpoints. The primary endpoints are safety endpoints that will be described in chapter 14.

13.4 Analysis Methodology for the Key Secondary Endpoints

There are no key secondary efficacy endpoints.

13.5 Analysis Methodology for the Secondary and Exploratory Endpoints

13.5.1 Short-term Efficacy Estimand

The short-term efficacy estimand is the mean change from Baseline in the weekly number of attacks (Weeks 1-4) for participants with chronic cluster headache receiving IV infusion of eptinezumab 400 mg every 12 weeks, without the use of transitional treatment (GON block and oral steroids), and regardless of the use of abortive and preventive medication for cluster headache, and infusion interruption or termination before full dose is received.

Clinical Question of Interest

The clinical question of interest is changes in cluster headache symptoms within the first 4 weeks after infusion with eptinezumab 400 mg.

Attributes of the Short-term Efficacy Estimand

The short-term efficacy estimand has the following attributes:

- The **treatment condition of interest** will be IV infusion of eptinezumab 400 mg every 12 weeks, with or without the use of abortive and preventive medication for cluster headache
- The **population of interest** will be participants with cCH
- The **endpoint to be obtained to address the clinical question** is change from Baseline in the weekly number of attacks (Weeks 1-4)
- The **intercurrent event** use of transitional treatment will be addressed by a hypothetical strategy estimating the efficacy, in the hypothetical scenario where no transitional treatment is available, while interruption or termination of IMP such that full dose is not received will be addressed by a treatment policy strategy
- The **population level summary** will be the mean change across weeks 1-4

13.5.1.1 Rationale for the Short-term Efficacy Estimand

The number of weekly attacks is considered a good measure of the impact of IV infusion of eptinezumab 400 mg every 12 weeks, since it captures an important part of the symptoms for cluster headache and therefore change from Baseline in the average number of weekly attacks will be used as the endpoint for the efficacy estimand described in details in section 13.5.1.

Justification of Treatment Condition of Interest

The use of abortive medication (triptans and oxygen) is included in the treatment condition of interest because abortive medication is taken after an attack begins to affect that specific attack. It is not expected that the use of abortive medication will affect the number of attacks following an attack where abortive medication was taken. Thus, the use of abortive medication is not considered to be an intercurrent event.

The use of preventive medication is included in the treatment condition of interest because eptinezumab is expected to be used with or without other preventive medication for participants suffering from chronic cluster headache. Furthermore, though the use of preventive medication could influence the number of attacks, the potential effect is expected to be limited in a chronic cluster headache population. Thus, the use of preventive medication is not considered to be an intercurrent event.

Intercurrent Events

The following intercurrent events, occurring after treatment initiation and potentially affecting either the interpretation or the existence of the measurements associated with the clinical question of interest, are considered.

- Use of transitional treatment (GON block and oral steroids) – hypothetical strategy

Use of transitional treatment could change the disease status considerably, and thus influence the number of attacks. In a study, 35% of the participants taking the oral steroid prednisone experienced a complete cessation of cluster headache attacks after 7 days compared to 7% in the placebo group and 49% taking prednisone experience at least a 50% reduction of cluster headache attacks compared to 15% for the placebo group after 7 days.¹ To get a clearer picture of the change in symptoms after infusion with eptinezumab, a hypothetical strategy has been chosen to address this, estimating the effect if no transitional treatment was available, using the 7 day limit¹ as described in section 23.2.1.5. Due to the expected positive effect of transitional treatment this is considered a conservative approach.

- Interruption or termination of IMP such that full dose is not received – treatment policy strategy

If an IMP is stopped prematurely (either temporarily or completely) the consequence is that the participant did not receive all of the intended dose of eptinezumab and it could be expected that the potential effect of eptinezumab could be decreased due to the lower dose. To be conservative, a treatment policy strategy is used to address this.

